## 3.5 Exploratory Endpoints

Change and percent change from baseline at Week 12 in the following:

- Plasma glucose (fasting and 2-hour PPG);

Confidential

Page 9 of 38

Version 1.3, July 23, 2019 Statistical Analysis Plan

- HOMA-IR index;

## 4 Study Design

## 4.1 Study Design

This is a Phase 2, randomized, double-blind, parallel-group, multicenter study of Bempedoic Acid (BA) 180 mg and Ezetimibe (EZE) 10 mg FDC versus Placebo (PBO) and EZE 10 mg administered for 12 weeks in subjects with type 2 diabetes (T2D) and elevated LDL-C.

Approximately 234 male and female subjects with a history of T2D for at least 6 months and who meet the inclusion and exclusion criteria will be enrolled and randomized in a 1:1:1 ratio to receive FDC (n = 78) or EZE (n = 78) or PBO (n = 78).

The expected study duration is approximately 126 days, including an approximate 42-day screening period (Visit S1/Day -42, followed by a 5-week single-blind PBO run-in/lipid-modifying therapy (LMT) washout period from Day -35 to Day -1), an 84-day treatment period beginning at Visit T1/Day 1, and an EOS visit (Visit T3/Day 85).

		Screening and F	Run-in Period		Treatment Period	
Subj	Subjects with T2D, HbA1c 7-10%, LDL-C > 70 mg/dL at Visit S1			FDC (n=78) EZE (n=78) PBO		
		1-Week Screening	5-Week Single-Blind Placebo Run-In		(n=78) 12-Week Double-Blind Treatment Period	
Clinic Visits (Day)	↑ S1 (-42 ± 7	52 52	¢	↑ T1 (1)	↑ 12 (28±3)	(85 ±

Figure 1. Study 1002FDC-058 Study Design

T2D = type 2 diabetes; HbA1c = hemoglobin A1c; LDL-C = low-density lipoprotein cholesterol; LMT = lipid-modifying therapy; BA = bempedoic acid; EZE = ezetimibe; FDC = fixed dose combination.

Confidential

Page 10 of 38

Version 1.3, July 23, 2019 Statistical Analysis Plan

#### 4.2 Study Treatments and Assessments

Subjects will receive one FDC-matched PBO tablet and one EZE-matching PBO capsule once daily for  $35 \pm 3$  days during the run-in period prior to randomization.

Subjects will be randomized to receive treatment with:

- One (1) BA 180 mg + EZE 10 mg FDC tablet and 1 EZE-matching PBO capsule once daily for 84 ± 3 days, or
- One (1) EZE 10 mg over-encapsulated tablet and 1 FDC-matched PBO tablet once daily for 84 ± 3 days; or
- One (1) FDC-matched PBO tablet and 1 EZE-matching PBO capsule once daily for 84 ± 3 days.

All IMP will be taken orally, at a similar time (approximate 24-hour intervals), in the morning with or without food.

Confidential

Page 11 of 38

The investigational products are listed in Table 1 below:

	Investigational Medicinal Product					
Product Name:	Bempedoic Acid + Ezetimibe FDC Tablet	Ezetimibe Over- encapsulated Tablet	FDC-matched Placebo Tablet	Ezetimibe-matched Placebo Capsule		
Dosage Form:	Film-coated tablets	Over-encapsulated tablets	Film-coated tablets	Capsules		
Unit Dose:	180 mg bempedoic acid + 10 mg ezetimibe	10 mg	Not applicable	Not applicable		
Container	Blister cards with child resistant closures					
Route of Administration:Oral with water with ou without food		Oral with water with or without food	Oral with water with our without food	Oral with water with or without food		
Physical Description:						

FDC = Fixed Dose Combination

Subjects with a history of T2D for at least 6 months will be screened for eligibility at an initial screening visit (Visit S1), which will be conducted approximately 42 days before planned randomization into the study. Subjects who have an LDL-C level >70 mg/dL and who meet all other inclusion/exclusion criteria will be return for Visit S2 approximately 5 weeks prior to planned randomization into the study to washout of all LDL-C-lowering therapies and begin taking single-blind (subject) PBO. Subjects will return to the study site approximately 7 days before planned randomization into the study for Visit S3. Subjects who have an LDL-C level  $\geq$ 100 mg/dL and who continue to meet the study inclusion/exclusion criteria will be scheduled for their first treatment visit.

Subjects will report to the study site for the first treatment visit (Visit T1/Day 1) after a minimum 10-hour fast. Subjects who continue to meet the study inclusion/exclusion criteria will be randomized in a 1:1:1 ratio to receive either FDC (n = 78), EZE (n = 78), or PBO (n = 78) once daily for 12 weeks. Randomized subjects will return for clinic visits at Week 4 (Visit T2) and Week 12 (Visit T3/EOS). Subjects who withdraw from IMP treatment will be asked to continue to be followed for safety and efficacy using the protocol-specified visit schedule and procedures. Subjects will be dispensed IMP at Visit T1/Day 1 and will be instructed to take the IMP in the morning at 24-hour intervals, with approximately 8 ounces of water, after a minimum 10-hour fast (only water allowed) and to continue fasting for 1 hour after ingesting the IMP with or without food. For details of study assessments, see Appendix 1: Schedule of Events (Patient Visit Schedule).

## 4.3 Randomization and Blinding

Subjects will receive single-blind PBO beginning at visit S2 and concluding with last dose on Day -1 (the day prior to Visit T1) during the Run-in period.

During the Treatment period, subjects will receive double-blind IMP. On Day 1 (Visit T1), subjects will be randomized to receive either FDC or EZE or PBO, randomized 1:1:1. Interactive web response system (IWRS) will be used to dispense randomized assigned blinded study drug to the subjects

Sponsor, site personnel, contract research organization (CRO), and subject will all be unaware of subject's treatment assignment during the Treatment period.

Blinding of treatment must be maintained for all subjects unless, in the opinion of the investigator, the safety of the subject may be at risk. Only under the rarest of circumstances should the investigator consider breaking the blind and only when medical/supportive care cannot be provided without determining if the subject is receiving active drug treatment. In the event that the blind needs to be broken prior to completion of the study, the investigator should contact the appropriate Medical Monitor by telephone. If the blind must be broken prior to consultation with the Medical Monitor, contact must be made within 24 hours of breaking the blind.

Confidential

Page 13 of 38

Version 1.3, July 23, 2019 Statistical Analysis Plan

At the initiation of the study, the clinical site will be instructed on procedures for breaking the blind via the IWRS. In all cases of breaking the blind, the investigator must document in the subject's medical record the date, time, and reason for breaking the blind, and the names of personnel involved.

Post-randomization values for individual laboratory measures for LDL-C, hs-CRP, non-HDL-C, TC, TG, and HDL-C that may inadvertently suggest treatment assignment will not be available to personnel from the clinical site, the subject, the Sponsor, or the CRO.

## 4.4 Sample Size Justification

The sample size of approximately 78 subjects per treatment arm (1:1:1) in this study (234 subjects total) is selected to provide adequate power for each of the co-primary endpoint as well as the co-primary endpoint family as a whole.

## 4.5 Interim Analyses, Final Analyses and Unblinding

No interim analysis is planned for this study.

The final analysis will be performed after the database is locked, the treatment assignments are unblinded using the actual randomization, and the database released.

## 4.6 Changes from Protocol Planned Analyses

Not applicable.

## 5 Statistical and Analytical Plans

### 5.1 General Statistical Considerations

The BA + EZE FDC treatment group will be displayed in the tables, listings and figures (TLFs) as "BA (180 mg) + EZE (10 mg) FDC", the EZE 10 mg will be displayed as "Ezetimibe 10 mg" and Placebo group will be displayed as "PBO"

In general, all safety and PD data will be reported as observed. No imputation will be performed for missing data, except for the missing lipid efficacy data (Please refer to

Confidential

Page 14 of 38

Section 5.3.2 for more details). Descriptive statistics (n, mean, standard deviation [SD], Q1, Q3, median, minimum, and maximum) will be calculated for continuous data. Minimum and maximum will be presented same number of decimal places as reported/collected, one additional decimal place for mean and median, and two additional decimal places for SD.

Categorical data will be summarized using n and percentage based on number of nonmissing values. Percentage will be presented with one decimal place. The number of missing values will be presented as a separate category with no percentage, but only if 1 or more patients have missing data for the summary. Otherwise, all categories will be presented (even if no patients are counted in the category). Counts of zero in any category will be presented without percentage.

Listings will be sorted in the order of patient, assessment date and assessment (in order collected on CRF, unless specified otherwise). Dates will be presented in format DDMMMYYYY.

Relative day calculations will be [date of interest – relative date + (date of interest  $\geq$  relative date)]. This calculation will result in dates prior to the relative date being presented as negative days, and those occurring on or after the relative date as Day 1 or later, i.e., there will be no Day 0.

Baseline for fasting lipid parameters including LDL-C, TC, HDL-C, non-HDL-C, and Triglycerides are defined as the average of S3 and T1 values (last two non-missing values on or prior to Day 1). If only one value is available, the single value will be used as baseline. For other parameters including apoB and hs-CRP, the baseline is defined as the last value/result where assessment date is less than or equal to the date of first study treatment, unless otherwise specified. If last dose of study treatment is missing, then the date of last visit at which study assessments were obtained on CRF will be used in its place.

Visit	S1	S2	S3	T1	T2	T3/EOS
Slotted Study Week	-6	-5	-1	1	4	12
Target Study Day	-42	-35	-7	1	28	85
Study Day Range	[-∞, -39]	[-38, -21]	[-20, -1]	1	[2, 56]	[57, ∞]

The visit schedule and windows for assessments that occur at Baseline, Week 4, and Week 12 are shown below:

The visit schedule and windows for assessments that occur at Baseline and Week 12 only, are shown below:

#### Confidential

Page 15 of 38

Visit	S1	S2	S3	T1	T3/EOS
Slotted Study Week	-6	-5	-1	1	12
Target Study Day	-42	-35	-7	1	85
Study Day Range	[-∞, -39]	[-38, -21]	[-20, -1]	1	[2,∞]

#### 5.2 Statistical Analysis Plans

#### 5.2.1 Analysis Sets

#### 5.2.1.1 Full Analysis Set (FAS)

The Full Analysis Set (FAS) is defined as all randomized subjects who receive at least 1 dose of study drug. FAS will be used for pharmacodynamics analyses. Subjects in FAS will be analyzed as per their randomized treatment group regardless of actual treatment they received.

#### 5.2.1.2 Efficacy Analysis Set

The Efficacy Analysis Set (EAS) is defined as FAS excluding 3 study sites (Sites ). These sites were suspected of good clinical practice (GCP) violation in an earlier phase 3 study and are under investigation. Therefore, to ensure the integrity and quality of the data and related analyses, we will use the Efficacy Analysis Set for the primary efficacy analyses. We will also conduct sensitivity analysis for efficacy analyses using FAS.

#### 5.2.1.3 Treatment Completer Analysis Set

The Treatment Completer analysis set is a subset of the FAS excluding 3 sites (**1999**, **1999**) and will include subjects who complete 12 weeks of treatment as indicated on the end of treatment CRF.

#### 5.2.1.4 Safety Analysis Set

The Safety Analysis Set will include all subjects who randomized and received at least 1 dose of IMP. Subjects will be included in the treatment group that they actually received regardless of their randomized treatment.

#### 5.2.2 **Protocol Deviations**

A full list of protocol deviations will be compiled and reviewed by the Esperion team to define each deviation as "major" or "minor" before final database lock. Major deviations will be those that are judged to have an impact on the integrity of data or endanger subject rights, safety and/or welfare. All other deviations will be judged as minor.

Confidential

Page 16 of 38

Protocol deviation information will be displayed for the safety analysis set in a subject listing.

Major protocol deviation will be summarized by treatment and categories in a table.

#### 5.2.3 Patient Disposition

The number of patients screened, randomized and included in each analysis population, along with study completion status, will be summarized by treatment group as well as overall. In addition, the number of patients who withdraw from the study and withdraw from IMP will be summarized by discontinuation reason.

#### 5.2.4 Demographic and Baseline Characteristics

The following demographic and baseline characteristics will be summarized by treatment group, as well as overall, for the safety analysis set and for the FAS: age (years), age will be summarized as a continuous variable and by age group (<65, >=65), gender, race, ethnicity, height (cm), weight (kg), body mass index (kg/m^2), BMI group (< 25, 25 - < $30 \ge 30 \text{ kg/m}^2$ ), systolic and diastolic blood pressure (mmHg), fasting lipid parameters (TC [mg/dL], calculated LDL-C [mg/dL], HDL-C [mg/dL], non-HDL-C [mg/dL] and TGs [mg/dL]), apoB (mg/dL), hs-CRP (mg/dL), history of hypertension, eGFR category, tobacco history, alcohol history, and weekly average number of alcoholic drinks, hemoglobin A1C (HbA1C), fasting glucose, Diabetes mellitus duration, Diabetes mellitus duration categories  $(0 - \langle 5, 5 - \langle 10, \rangle = 10 \text{ years})$ , No. of prior diabetes mellitus therapies  $(0, 1, 2, \ge 3)$ , Type of prior diabetes mellitus therapies, Type of prior diabetes mellitus therapies ("Metformin", "Sulfonylurea" "No prior therapies indicated"). Data will be summarized using descriptive statistics for continuous variables and using counts and percentages for categorical variables by treatment group and overall.

The baseline estimated glomerular filtration rate (eGFR) categories are: normal:  $\geq$ 90 mL/min/1.73m^2; mild Renal Impairment: 60-89 mL/min/1.73m^2; moderate Renal Impairment: 30-59 mL/min/1.73m^2, and severe Renal Impairment (15-29 mL/min/1.73m^2).

#### 5.2.5 Subgroup Variables

Subgroups defined by below variables will be evaluated for safety and the primary and secondary efficacy endpoints. The reference level for each subgroup/covariate variable is indicated with (ref).

- 1) Gender (male (ref) vs. female)
- 2) Age (< 65 yrs.(ref) vs.  $\geq$ 65 yrs.)
- 3) Race (White vs. other)
- 4) Baseline LDL category (< 160mg/dL (ref) vs. ≥160 mg/dL)
- 5) Baseline HbA1C (the categories will be divided by median)
- 6) Years of T2D (0 <5, >=5 year)

Confidential

Page 17 of 38

In case the number of patients within a subgroup is too small, e.g. less than 5% of the overall population, the analyses may not be performed or the subgroup levels may be combined. Subgroup analysis will be conducted on primary endpoint and exploratory PD endpoint analyses.

#### 5.2.6 Medical History

General medical history and cardiovascular history/risk factors will be summarized by treatment group, as well as overall, for FAS population and presented in a by-patient listing. Where appropriate, terms will be coded using the Medical Dictionary for Regulatory Activities (MedDRA) Version 21.0 or later.

#### 5.2.7 Baseline Serology, Serum and Urine Pregnancy Test and TSH

Hepatitis B surface antigen (HBsAg), hepatitis C virus (HCV), and serum pregnancy test (only for females of childbearing potential), follicle stimulating hormone ([FSH], only for females who are < 55 years old and > 1 year without menses), urine pregnancy test Day 1 prior to randomization and thyroid-stimulating hormone (TSH) will be presented in a by-patient listing.

#### 5.2.8 **Prior and Concomitant Medications**

Prior medications are defined as medications that ended prior to the first dose of IMP. Concomitant medications are defined as medications that were ongoing at the time of first dose of IMP or new medications that started after first dose of IMP and within 30 days following the date of the last dose of IMP.

Medications will be coded using WHO Drug (March, 2018 or later). The use of prior or concomitant medications will be summarized by treatment group, as well as overall, for the safety analysis set according to Anatomical Therapeutic Chemical (ATC) class and coded medication name. Prior and concomitant medications will be listed for each patient.

#### 5.2.9 IMP Exposure and Compliance

The length of exposure to IMP (FDC, and EZE) will be calculated as the number of days from the first dose of double-blind IMP to the last dose of double-blind IMP, regardless if the patient missed one or more doses of IMP. Length of exposure will be summarized by treatment group using descriptive statistics for the safety analysis set. The length of exposure will be calculated as first dose of PBO to the last dose of PBO in respective periods.

Confidential

Page 18 of 38

The number and percentage of patients who were compliant with taking IMP will be summarized by treatment group for the safety analysis set for the following categories 0 < 80%; >= 80%.

Overall compliance will be calculated as: 100\* (Total Number of Tablets Dispensed – Total Number of Tablets Returned) / (2\*Treatment Duration in Days). The IMP administration and compliance data, including reasons for poor compliance, if noted in CRF will be listed for each patient.

Same approach will be applied in calculating exposure and compliance for single-blinded PBO run-in period. Listing and table will be provided separately to IMP during treatment period.

## 5.3 Primary Efficacy Endpoints and Analyses

For all efficacy analyses, the EAS will be used, with patients included in their randomized group, regardless of the treatment they actually received.

#### **5.3.1** Analysis for the Efficacy Parameters

For the primary efficacy analysis, percent change in LDL-C at week 12 and the secondary endpoints of percent change in hs-CRP, non-HDL-C, HDL-C, TC, TG, and apoB at week 12 will be analyzed using the analysis of covariance (ANCOVA) method. The ANCOVA model will include treatment as factor, and baseline value as covariate. The model assumptions for ANCOVA will be assessed and if these assumptions are severely violated, alternative non-parametric approach will be performed.

An example SAS code for ANCOVA analysis is shown as below:

PROC MIXED DATA=adeff; class armcd; model pchg = blres armcd / solution ddfm=kenwardroger; ; lsmeans armcd / diff=control ('ref') cl;

The least square mean (LSM) and standard error (SE) for percent change estimate will be provided for all the treatment groups, along with PBO-corrected LSM, its 95% confidence interval (CI) and associated p-value.

For hs-CRP and TG, a non-parametric (Wilcoxon rank-sum test) analysis with Hodges-Lehmann estimates and confidence interval will also be performed because based on historical knowledge, publication precedence (Brendan et al., 2006) and recent data available, hs-CRP and TG are known to be skewed by extreme values and have nonnormal distribution.

Confidential

Page 19 of 38

Version 1.3, July 23, 2019 Statistical Analysis Plan

For other secondary endpoints, number and percent of subjects with LDL-C < 70mg/dL at week 12 will be tabulated by treatment. Number and percent of subjects LDL-C reduction  $\geq$  50% from baseline to Week 12 will be tabulated by treatment. Chi-sq test or fisher exact test will be performed between the FDC-treated arm and EZE-treated arm and PBO-treated arm for those two endpoints. Only observed data will be used, i.e. the denominator will be number of subjects who have LDL-C value at perspective time point. Efficacy data (actual value, change and percent change from baseline) from all visits will be presented using descriptive statistics using both conventional and standard units. A figure of mean (+/- SE) value or median (IQR) as appropriate, over time will be provided for these efficacy parameters.

Efficacy data will also be listed.

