14.5. Study Endpoints

The primary objectives of this study are demonstrated by 2 co-primary endpoints:

- Percent change in LDL-C from baseline at Week 12 in FDC-treated arm compared to PBO-treated arm;
- Percent change in LDL-C from baseline at Week 12 in FDC-treated arm compared to EZE-treated arm.

The study is considered to have successfully demonstrated its primary objective if both co-primary endpoints achieve statistical significance.

Secondary Endpoints

- Percent change from baseline at Week 12 in parameters below between the FDC treated arm and EZE treated arm and PBO treated arm:
 - hs-CRP;
 - Non-HDL-C;
 - TC;
 - apoB;
 - TG;
 - HDL-C;
- Proportion of subjects attaining LDL-C <70 mg/dL at Week 12 in FDC-treated arm and EZE-treated arm and PBO-treated arm;
- Proportion of subjects achieving LDL-C reductions $\geq 50\%$ from baseline at Week 12 in FDC-treated arm and EZE-treated arm and PBO-treated arm.

Safety Endpoints

- Subject incidence of TEAE;
- Safety laboratory values, PE findings, and vital signs.

Exploratory Assessments

- Percent change from baseline at [REDACTED] Week 12 in parameters below between the FDC-treated arm and EZE-treated arm and PBO-treated arm:
 - HbA_{1C};
 - Plasma glucose (fasting and 2-hour post-prandial);

[REDACTED]

[REDACTED]
– HOMA-IR index;
[REDACTED]

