14.6. Pharmacodynamic Analyses

Descriptive statistics (number, mean, median, standard deviation, minimum, and maximum) will be used to summarize LDL-C, TC, HDL-C, non-HDL-C, TGs, apoB, hs-CRP, glucose, [REDACTED], [REDACTED] HbA_{1C}, HOMA-IR, [REDACTED], and 2-hour PPG levels at each assessment by treatment group and to summarize the change from baseline and the percent change from baseline by treatment group at each postbaseline assessment.

The primary and secondary efficacy endpoint will be analyzed using analysis of covariance (ANCOVA), with treatment group as a factor and baseline value as a covariate. The ANCOVA will be performed using the FAS, with subjects included in their randomized treatment group regardless of the treatment they actually received. Subjects who are missing their Week 12 LDL-C will have their Week 12 value imputed by last postbaseline observation carried forward (LOCF). The least squares mean (LSM) and standard error (SE) for percent change estimate will be provided for both treatment groups, along with the PBO-corrected LSM, its 95% confidence interval (CI) and associated p-value. We will analyze observed data and LOCF data separately.

The same analysis will be performed as sensitivity analysis on treatment completer set for primary and secondary efficacy endpoints.

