## 3 Study Objectives and Endpoints

## 3.1 Objectives

The co-primary objectives of this study are:

- To assess the efficacy of FDC versus PBO on LDL-C lowering in subjects with T2D treated for 12 weeks; and
- To assess the efficacy of FDC versus EZE on LDL-C lowering in subjects with T2D treated for 12 weeks

The secondary objectives are:

- To assess the efficacy of EZE versus PBO on LDL-C lowering in subjects with T2D treated for 12 weeks;
- To assess the efficacy of FDC versus PBO, FDC versus EZE, and EZE versus PBO on high-sensitivity C-reactive protein (hs-CRP), non-HDL-C, total cholesterol (TC), apolipoprotein B (apoB), TG, and HDL-C in subjects with T2D treated for 12 weeks;
- To assess the effect of FDC, EZE, and PBO on percent of subjects achieving LDL-C level <70 mg/dL;
- To assess the effect of FDC, EZE, and PBO on percent of subjects achieving LDL-C reduction ≥50%; and
- To characterize the safety and tolerability of FDC, EZE, and PBO in subjects with T2D treated for 12 weeks.

Confidential

Page 8 of 38

Version 1.3, July 23, 2019 Statistical Analysis Plan

Exploratory objective of this study is:

To assess the effect of FDC versus PBO and EZE on hemoglobin A1C (HbA1C), fasting glucose, homeostatic model assessment of insulin sensitivity (HOMA-IR) and and 2-hour postprandial glucose (PPG) in subjects with T2D treated for 12 weeks.

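### Does the primary analysis leave out the co-primary FDC versus EZE test by naming only placebo-corrected results?

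*SAP*

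**What the plan says.** SAP 3.1 lists as its second co-primary objective "To assess the efficacy of FDC versus EZE on LDL-C lowering in subjects with T2D treated for 12 weeks". Protocol 14.5 defines the matching co-primary endpoint as "Percent change in LDL-C from baseline at Week 12 in FDC-treated arm compared to EZE-treated arm" and sets the success rule: "The study is considered to have successfully demonstrated its primary objective if both co-primary endpoints achieve statistical significance".

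SAP 5.3.1 specifies the model: "The ANCOVA model will include treatment as factor, and baseline value as covariate". It asks for the least squares mean and standard error in all treatment groups, "along with PBO-corrected LSM, its 95% confidence interval (CI) and associated p-value". The code is introduced with "An example SAS code for ANCOVA analysis is shown as below", and its contrast line is "lsmeans armcd / diff=control ('ref') cl".

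Protocol 14.6 has a similar sentence, in which the estimates "will be provided for both treatment groups, along with the PBO-corrected LSM, its 95% confidence interval (CI) and associated p-value". Further down SAP 5.3.1, the tests for the two LDL-C responder endpoints name the FDC, EZE and PBO arms.

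**The concern.** Three arms give three pairwise differences. A single-reference `DIFF=CONTROL` statement returns two. If the reference is PBO, as the reporting sentence suggests, those are FDC minus PBO and EZE minus PBO. The second is only a secondary objective, while FDC minus EZE, on which half of the success rule rests, is not listed. The same holds for the FDC versus EZE objectives on hs-CRP, non-HDL-C, TC, apoB, TG and HDL-C. Protocol 14.6 even speaks of two treatment groups in a three-arm trial, and the SAP does not repeat the success rule.

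If the listed outputs really were all that was produced, the stakes would be high. FDC versus EZE is the only comparison that isolates what bempedoic acid adds to ezetimibe, and the placebo contrasts cannot answer that question.

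**Working it through.** **1. Which contrasts the text covers.**

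| Comparison (LDL-C) | Status in the documents | Listed output, SAP 5.3.1 | From the specified model |
|---|---|---|---|
| FDC − PBO | Co-primary | Yes | Yes |
| FDC − EZE | Co-primary | Not listed | Yes |
| EZE − PBO | Secondary | Yes | Yes |

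Protocol 14.5 defines the second co-primary endpoint as the FDC versus EZE comparison itself, and protocol 14.6 assigns the primary endpoint to ANCOVA. Together they call for this contrast. In the SAP code `ref` is a placeholder, not set to PBO. With EZE as the reference, the same line returns FDC − EZE.

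**2. Whether placebo contrasts could stand in.** They could not. Assumed inputs, since the available text gives no effect size or SD: 78 per arm (SAP 4.4), residual SD 20, EZE 20 points below PBO, two-sided 0.05, 2,000 simulated trials per row, three-arm ANCOVA.

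| True FDC − EZE | Both PBO contrasts significant | FDC − EZE significant |
|---|---|---|
| 0 | 100% | 5.3% |
| −5 | 100% | 35.1% |
| −10 | 100% | 86.1% |

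So the FDC − EZE test has to be run. The question is whether the plan leaves that in doubt.

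**3. Whether an analyst would have a choice.** The model, covariate, analysis set and imputation are fixed in SAP 5.2 and 5.3. Given those, FDC − EZE is one linear combination of the fitted coefficients. Requesting all pairwise differences, or rerunning the line with EZE as reference, gives the same unadjusted estimate, interval and p-value.

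**4. Whether the required outputs already carry it.** The point estimate is exact either way:

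LSM(FDC) − LSM(EZE) = [LSM(FDC) − LSM(PBO)] − [LSM(EZE) − LSM(PBO)].

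For the standard error, let s² be the residual variance, n the arm size, dᵢ the deviation of arm i's mean baseline from the overall mean, and S the within-arm baseline sum of squares.

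- Model: Var(FDC − EZE) = s²[2/n + (d_FDC − d_EZE)²/S].
- Rebuilt from the arm-level SEs: SE_FDC² + SE_EZE² = s²[2/n + (d_FDC² + d_EZE²)/S].

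They differ only by 2·s²·d_FDC·d_EZE/S, which under randomization reflects chance baseline imbalance. I simulated 3,000 trials with 78 per arm, SD 15, a true difference of 8 points, and baseline mean 145, SD 28 and slope −0.1 (all but the arm size assumed). The rebuilt SE averaged 0.999 times the model SE and stayed within about 2% of it in every run. Power was about 91% by either route.

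**5. The pessimistic figure.** With SD 15, SE(FDC − EZE) = 15 × √(2/78) = 2.40. Treating the two placebo contrasts as independent gives 2.40 × √2 = 3.40, and power at 8 points falls from Φ(8/2.40 − 1.96) ≈ 0.91 to Φ(8/3.40 − 1.96) ≈ 0.65. The arithmetic is right, but it describes a mistake: it ignores the shared placebo arm and the arm-level SEs that the SAP requires. Nobody plans to analyse the trial that way.

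**The case for a change.** The strongest case for a change is that a co-primary test should not rest on a programmer's inference. A SAP exists to fix, before unblinding, the numbers that decide success, and a reader of section 5.3.1 cannot find one of the two. The SAP takes precedence over the protocol on analysis, yet repeats neither the success rule nor a test level. The responder tests in the same section name the EZE arm, so the sentence on continuous endpoints is out of step with its neighbour. The correction would cost one line of code and a few sentences.

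Part of this stands. The list of outputs is incomplete, and the two-group wording in protocol 14.6 is a slip, which the SAP replaces with wording that covers all groups. The rest does not carry. The SAP overrides the protocol only where the two differ, and silence is not a difference. SAP 4.6 records no changes from the protocol's planned analyses, so the success rule in protocol 14.5 remains in force. The 95% intervals point to a two-sided 0.05 level, and requiring both tests to be significant calls for no multiplicity adjustment. SAP 4.4 sizes the trial for each co-primary endpoint and for the pair, which makes sense only if both are tested. The inference left to the programmer is to report a comparison that SAP 3.1 names as co-primary, from a model that already contains it.

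**Conclusion.** No change is needed. SAP 5.3.1 and protocol 14.6 omit the FDC − EZE difference, its interval and its p-value from the outputs they list, but nothing in either document excludes that test or would make it come out wrong. The comparison, model, arms and success rule are all stated, and a competent analyst would fill the gap in only one way. The same reasoning covers the six continuous secondary parameters, whose FDC versus EZE comparisons are named in SAP 3.1.

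The effect on estimates, error rates and power is nil as long as the contrast is taken from the three-arm model, as specified. This rests on reading the code as the example it is called, and the placebo-corrected sentence as a partial list rather than a restriction. The simulated figures use assumed SDs and effects and serve for scale only; the conclusion does not depend on them.
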